10.11 APPENDIX 11: ABBREVIATIONS

ADA:	anti-drug antibody
ADCC:	antibody-dependent cellular cytotoxicity
ADCP:	antibody-dependent cellular phagocytosis
AE:	adverse event
AESI:	adverse event of special interest
ALT:	alanine aminotransferase
AMR:	antibody mediated rejection
ANC:	absolute neutrophil count
AST:	aspartate aminotransferase
CD:	cluster of differentiation
CDC:	complement dependent cytotoxicity
CKD:	chronic kidney disease
CMV:	cytomegalovirus
CONSORT:	Consolidated Standards of Reporting Trials
cPRA:	calculated panel reactive antibodies
CRF:	case report form
CTCAE:	common terminology criteria for adverse events
DL-1:	dose level minus 1
DNA:	deoxyribonucleic acid
DoR:	duration of response
DRE:	Disease-related event
DSA:	donor-specific antibody
E/D:	early discontinuation
EBV:	Epstein-Barr virus
ECG:	electrocardiogram
eCRF:	electronic case report form
ESRD:	end stage renal disease
FSH:	follicle stimulating hormone
FUP:	follow-up period
GCP:	Good Clinical Practice
G-CSF:	granulocyte-colony stimulating factor
GVHD:	graft-versus-host-disease
HBsAg:	hepatitis B surface antigen
HBV:	hepatitis B virus
HIV:	human immunodeficiency virus
HLA:	human leukocyte antigen
HRT:	hormonal replacement therapy
IAT:	indirect antiglobulin test
ICF:	informed consent form
ICH:	International Council for Harmonisation
IEC:	Independent Ethics Committee
IgG1:	immunoglobulinG1
IMP:	investigational medical product

IR:	infusion reactions
IRB:	Institutional Review Board
IV:	intravenous
IVIG:	intravenous immunoglobulin
KAS:	Kidney Allocation System
LCD:	likelihood of compatible donor
mAb:	monoclonal antibody
MFI:	mean fluorescence intensity
NCI:	National Cancer Institute
NIMP:	noninvestigational medicinal product
NK-cell:	natural killer cell
PD:	pharmacodynamic
PK:	pharmacokinetic
PO:	oral route
Q2W:	once every 2 weeks
QW:	once weekly
RNA:	ribonucleic acid
RR:	response rate
SAB:	single antigen bead
SAE:	serious adverse event
SAP:	statistical analysis plan
SD:	starting dose
SoA:	Schedule of Activities
TCMR:	T-cell mediated rejection
TEAE:	treatment emergent adverse events
ULN:	upper limit of normal
US:	United States
WOCBP:	women of childbearing potential

10.12 APPENDIX 12: PROTOCOL AMENDMENT HISTORY

The Protocol Amendment Summary of Changes Table for the current amendment is located directly before the Table of Contents (TOC).

10.12.1 Amended protocol 01 (23 July 2020)

This amended protocol 01 (amendment 01) is considered to be substantial based on the criteria set forth in Article 10(a) of Directive 2001/20/EC of the European Parliament and the Council of the European Union.

OVERALL RATIONALE FOR THE AMENDMENT

Protocol amendment summary of changes table

Section # and Name	Description of Change	Brief Rationale
1.1 Synopsis; 2.3.3 Preventive measures to minimize the risk of isatuximab; 6.1 Study intervention(s) administered	Ranitidine is removed from standard premedication regimen and will be considered as per medical judgement of the Investigator. Criteria for optional premedication is simplified to base on no IR upon 4 consecutive infusions.	To provide option to adapt the premedication depending on individual situation.
1.3 SoA (footnote f); 5.2 Exclusion criteria; 6.5 Concomitant therapy; 6.6.3 General guidelines for the management of adverse events; 10.2 Appendix 2 Clinical laboratory tests	Included detailed guidance relating to viral reactivation monitoring and risks. As a new footnote "f" was implemented, numbering of following footnotes were shifted accordingly.	To clarify monitoring and risks related to viral reactivation.
1.3 SoA (footnote i)	Added indirect Coombs tests after treatment period during Site Visit follow-up period (FUP) if C2D1 is positive.	To investigate duration of blood typing interference following termination of isatuximab treatment.
1.3 SoA (Blood draw for functional immune cell assay)	Add sample collection during Site Visit FUP Week 1 or E/D if C3D1 sample not collected.	To ensure a post-treatment sample is collected in case C3D1 sample is not collected or if patient discontinued treatment prior to C3D1.
1.3.1.1 Treatment period: Cycle 1 (rich sampling)	C1D1 EOI+4h (\pm 30 min) timepoint is modified to EOI+1h (+30 min) timepoint.	Modification of sample collection timepoint to reduce wait time/burden for study participants.
1.3.1.1 Treatment period: Cycle 1 (rich sampling) 1.3.1.2 Treatment period: Cycle 2 and beyond (sparse sampling)	Addition of allowing PK/ADA sample to be collected at participant's home by a health care professional (depending on local arrangements).	To provide flexibility and potentially reduce site visit for study participants.
2.2 Background	Updates of isatuximab approval status and number of treated patients.	To provide updates aligned with updates of isatuximab IB ed11.
2.3.3 Preventive measures to minimize the risk of isatuximab; 6.1 Study intervention(s) administered; 6.6.4 General guidelines for the management of infusion reactions	Updated infusion rates based on fixed volume infusion method.	Switching to faster infusion schedule with a fixed distribution volume will reduce hospital chair time (particularly in some specific challenging situations like pandemic restrictions) and increase convenience for patients and sites.

Section # and Name	Description of Change	Brief Rationale
5.1 Inclusion criteria	For participants in Cohort B (I04): cPRA upper limit corrected from 99.80% to 99.89%.	Correction of typographical error.
5.2 Exclusion criteria	E14: Added obinutuzumab to require 6 months washout period.	Inclusion of obinutuzumab in E14 as it has similar mechanism of action as rituximab which is mentioned in the original E14.
7.1.2 Temporary discontinuation	The following text was added: "Temporary intervention discontinuation may be considered by the Treating Investigator because of suspected AEs or disruption of the clinical trial due to a regional or national emergency declared by a governmental agency (Section 10.13). For all temporary intervention discontinuations, duration should be recorded by the Investigator in the appropriate pages of the eCRF".	Include flexibility and ease of continuation of study during regional or national emergency such as Covid-19.
8.0 Study assessments and procedures		
9.4 Statistical analyses		
10.1.3 Informed consent process		
10.13 Appendix 13. Contingency measures for a regional or national emergency that is declared by a governmental agency.	"Onsite visits" changed to "telephone/remote visits" for flexibility to continue the trial during regional or national emergency such as covid-19 pandemic. Contingency Measures for a regional or national emergency are added.	
6.6.4 General guidelines for the management of infusion reactions	Updated management guideline on Grade 2 and 3 IR including permanent discontinuation of study treatment at third IR.	Clinical management of Grade 3 infusion reaction was updated to align with isatuximab IB ed11. Re-infusion rates following grades 2 and 3 infusion reactions were updated to align with the faster infusion protocol.
8.3.7 Disease-related events and/or disease-related outcomes not qualifying as AEs or SAEs	"AE or" was added to the sentence: "However, if either of the following conditions applies, then the event must be recorded and reported as an AE or SAE (instead of a DRE):"	Clarification.
10.2 Appendix 2 Clinical laboratory tests	Pregnancy test frequency is corrected to be consistent with SoA.	Pregnancy test frequency was not consistent with Section 1.3 SoA (Screening, C2D1, C3D1 were missing).
All document	Minor editorial and format changes. List of abbreviations updated.	Accuracy.

10.13 APPENDIX 13: CONTINGENCY MEASURES FOR A REGIONAL OR NATIONAL EMERGENCY THAT IS DECLARED BY A GOVERNMENTAL AGENCY

Continuation of the study in the event of a regional or national emergency declared by a governmental agency:

A regional or national emergency declared by a governmental agency (eg, public health emergency, natural disaster, epidemic/pandemic, terrorist attack) may prevent access to the clinical trial site.

Contingency procedures are suggested below and in [Section 8](#) for an emergency that prevents access to the study site, to ensure the safety of the participants, to consider continuity of the clinical study conduct, protect trial integrity, and assist in maintaining compliance with Good Clinical Practice in Conduct of Clinical Trials Guidance. Sponsor agreement MUST be obtained prior to the implementation of these procedures for the duration of the emergency.

During the emergency, if the site will be unable to adequately follow protocol mandated procedures, alternative treatment outside the clinical trial should be proposed, and screening and administration of study intervention may be temporarily delayed.

Procedures to be considered in the event of a regional or national emergency declared by a governmental agency:

- If onsite visits are not possible, remote visits (eg, with home nurses, home health vendor, etc.) may be planned for the collection of possible safety and/or efficacy data. For example, patient interview for medical history/prior medications could be performed by phone, local safety labs and some efficacy assessments could be performed off-site/at the participant's home (eg, home nursing) if agreed by patient and permissible per local regulations.
- If onsite visits are not possible visit windows may be extended for assessment of safety and/or efficacy data that cannot be obtained remotely, if needed (eg, ± 14 days for visits).
- Use of local clinic or laboratory locations may be allowed.

Contingencies implemented due to emergency will be documented.

The impact of the regional or national emergency declared by a governmental agency on study conduct will be summarized (eg, study discontinuation or discontinuation/delay/omission of the intervention due to the emergency). Any additional analyses and methods required to evaluate the impact on efficacy (eg, missing data due to the emergency) and safety will be detailed in the SAP.

For a regional or national emergency declared by a governmental agency, contingency procedures may be implemented for the duration of the emergency. The participant or their legally authorized representative should be verbally informed prior to initiating any changes that are to be implemented for the duration of the emergency (eg. study visit delays/treatment extension, use of local labs).

2	Current version	Criteria for cPRA reduction is corrected from "at least 50% increase of likelihood" to "at least 100% increase of likelihood".	To clarify that the target cPRA is defined as achieving at least 100% increase in the likelihood of finding a compatible donor, but this will not affect any mathematical derivations/calculations already in place.

1 INTRODUCTION

1.1 STUDY DESIGN

This is a Phase 1b/2 open-label, non-randomized, multi-center study to evaluate the safety, pharmacokinetics (PK), and preliminary efficacy of isatuximab in patients awaiting kidney transplantation.

Patients sensitized to the human leukocyte antigen (HLA) with a high calculated panel reactive antibodies (cPRA) have low likelihood of finding a compatible donor. Currently no approved or standard therapy is available for desensitization. An effective desensitization therapy with a durable response has the potential to increase the likelihood for transplant candidates to find a compatible donor, reduce time on dialysis, and a better clinical outcome.

The study will be conducted in 2 phases (see [Figure 1](#) for study design schema).

Phase 1 (safety run-in)

As the safety profile of isatuximab is well-established, Phase 1 (safety run-in) is designed to characterize the safety and tolerability of isatuximab in patients with chronic kidney disease (CKD), and to confirm the Phase 2 dose in this patient population. A minimum of 6 safety evaluable participants with cPRA $\geq 80\%$ will be enrolled at the dose level to be tested without interruption in Phase 1. In order to be considered as safety evaluable, participants must have received at least 90% of the planned cumulative doses of the first cycle (unless they discontinue investigational medicinal product (IMP) due to pre-defined unacceptable toxicity).

Pre-defined unacceptable toxicity is defined as any verified Grade 4 adverse events (AEs) or laboratory abnormalities (except infusion reactions (IRs)) occurring during the first cycle of treatment, unless solely due to the underlying disease or due to a cause obviously unrelated to IMP, if confirmed by the Sponsor and recruiting Investigators.

The starting dose of IMP is 10 mg/kg QW for 4 weeks followed by Q2W. If the starting dose is determined not to be sufficiently well-tolerated, 6 additional (minimum) safety evaluable participants will be enrolled at dose level (DL) -1 (ie, 5 mg/kg QW for 4 weeks followed by Q2W) (see protocol Table 4 for details on the DLs and schedule for Phase 1).

Overall safety monitoring will also be performed throughout the conduct of the study. The totality of the safety findings, including all AEs occurring during treatment, unless solely due to the underlying disease or due to a cause obviously unrelated to IMP, will be taken into consideration for confirming the Phase 2 dose. Phase 2 of the study will be initiated after 6 safety evaluable participants have completed first cycle observation period where the dose level is determined to be sufficiently well-tolerated.

Upon completion of the first cycle safety observation period for each participant enrolled in Phase 1, participants will continue study procedures until study completion.

Phase 2

Phase 2 is designed to assess preliminary efficacy of isatuximab in desensitizing HLA sensitized patients awaiting kidney transplantation, which includes assessing change in cPRA and anti-HLA antibody levels. Approximately 24 to 36 participants (Phase 1 and Phase 2) are expected to be enrolled if the starting dose (10 mg/kg) is retained as the Phase 2 dose, or approximately 30 to 42 participants are expected to be enrolled if DL-1 (5 mg/kg) is the Phase 2 dose.

In Phase 2, two cohorts will be included:

Cohort A: Participants with cPRA $\geq 99.90\%$; active candidates on the kidney waitlist. Up to 6 participants with living donor can be enrolled into Cohort A.

Cohort B: Participants with cPRA 80.00% to 99.89%; active candidates on the kidney waitlist with no living donor cleared for donation.

The study will have a screening period of up to 28 days, a treatment period of up to 12 weeks, a site visit follow-up period (FUP) of up to 26 weeks, and an extended FUP which include telephone contacts every 90 days and information collection until study cut-off, death, or lost to follow-up. The study cut-off is planned at 26 weeks after the last participant completes the treatment period, or when the last ongoing participant is lost to follow-up, whichever is earlier. The Sponsor (Sanofi) may choose to extend the study cut-off date depending on the enrollment rate observed to facilitate adequate follow-up data collection. Participants who wish to proceed to transplantation when a compatible donor becomes available while on study must discontinue IMP immediately, complete an early discontinuation (E/D) visit prior to transplantation if clinically feasible, and proceed to extended FUP. The study duration that involves site visit per participant (ie, screening, treatment, site visit FUP) will be approximately 42 weeks. The study duration including extended FUP per participant will be approximately 78 weeks (depending when the participant is enrolled).

Treatment period: The cycle duration is 28 days and a complete treatment period is comprised of 3 cycles of IMP treatment. Participants will continue treatment until receiving 3 cycles of IMP, unacceptable AE per Investigator's judgment, or participants' decision to stop the treatment.

Site visit FUP: Participants completing the treatment period and who are able to remain on study will return to the study sites for study procedures.

Extended FUP: The following participants will be followed-up every 90 days by phone calls, until study cut-off date, death, or lost to follow-up, whichever comes first:

- Participants who completed or discontinued from site visit FUP
- Participants who proceed to transplantation during treatment period or site visit FUP.

During extended FUP, specified information per protocol will also be collected by study site (see protocol section 1.3).

Below figures show the study schema and duration of study period:

Figure 1 - Graphical study design

[figure not shown]
[figure not shown]

Figure 2 - Duration of study period (per participant)

Details on schedule of activities (SoA) are provided in protocol section 1.3.

1.2 OBJECTIVE AND ENDPOINTS

Table 1 - Objectives and endpoints

Objectives	Endpoints
Primary	

Phase 1: To characterize the safety and tolerability of isatuximab in kidney transplant candidates.Phase 2: To evaluate the efficacy of isatuximab in desensitization of patients awaiting kidney transplantation.	
AEs/serious AEs (SAEs) and laboratory abnormalities.Response rate (RR defined as the proportion of participants meeting at least one of the predefined desensitization efficacy criteria, from baseline up to 26 weeks after treatment period, measured by single antigen bead (SAB) assay per central laboratory assessment as follows:

Objectives	Endpoints
	
1. Reduction in cPRA resulting in at least 100% increase of likelihood of finding a compatible donor (for target cPRA, see protocol section 10.9).2. Reduction in antibody titer ($\geq 75\%$ reduction from baseline) to achieve target cPRA (see protocol section 10.9).3. Elimination of ≥ 1 anti-HLA-antibody (ie, mean fluorescence intensity [MFI] reduced to < 2000) as measured by a SAB assay, for antibodies with baseline MFI ≥ 3000.
Secondary	

• Phase 2: To characterize the safety profile of isatuximab in kidney transplant candidates.• To characterize the PK profile of isatuximab in kidney transplant candidates.• To evaluate the immunogenicity of isatuximab.• To assess the overall efficacy of isatuximab in desensitization of patients awaiting kidney transplantation.	
• AEs/SAEs, and laboratory abnormalities.• PK parameters of isatuximab (see protocol Table 7)• Incidence of anti-drug antibodies (ADA) against isatuximab.• Duration of response (DoR) per central laboratory assessment.• Proportions of participants and duration achieving target cPRA per local laboratory assessment.• Number of anti-HLA-antibody with baseline MFI ≥ 3000 reduced to < 2000 as measured in a SAB assay per central laboratory assessment.• Transplantability including time to first transplant offer, time to transplant, and number of transplant offers, if applicable.• Time to first antibody mediated rejection (AMR) episode and rate of AMR, if applicable.• Graft survival at 6 months post-transplant, if applicable.
Tertiary/exploratory	

• To assess other preliminary efficacy of isatuximab in desensitization of patients awaiting kidney transplantation.• To assess the biological effects of isatuximab on immune cell populations and identify potential predictive and/or PD biomarkers• To perform PK/PD analysis.	      

1.2.1 Estimands

Primary estimand defined for the main efficacy endpoint is summarized in below [Table 2](#).

Table 2 - Summary of primary estimand for main efficacy endpoint

Endpoint Category (estimand)	Estimands			
	Endpoint	Population	Intercurrent event(s) handling strategy	Population-level summary (Analysis and missing data handling)
Primary efficacy objective: Phase 2: To evaluate the efficacy of isatuximab in desensitization of patients awaiting kidney transplantation				
Primary efficacy endpoint (Estimand 1)	Response rate	Efficacy-evaluable	Interruption/discontinuation of study intervention: Response rate will be analyzed regardless of intervention discontinuation (treatment policy)	Response rate, defined as proportion of participants meeting at least one of the predefined desensitization efficacy criteria, from baseline up to 26 weeks after treatment period and two-sided 95% confidence intervals using the Clopper-Pearson method (1)

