9.3 POPULATIONS FOR ANALYSES

For purposes of analysis, the following populations are defined ([Table 8](#)):

Table 8 - Populations for analyses

Population	Description
Screened	All participants who sign the ICF.
All Treated	Includes all participants who receive at least 1 dose of isatuximab. This population is the primary population for the analyses of safety parameters, unless otherwise noted. All analyses using this population will be based on the dose level actually received.
Safety Evaluable (Phase 1)	Includes all participants enrolled in Phase 1 who receive $\geq 90\%$ planned cumulative doses of isatuximab within Cycle 1 (unless IMP is discontinued due to pre-defined unacceptable toxicity).
Efficacy Evaluable	Includes All Treated Population who fulfill the study eligibility criteria, with an evaluable baseline and at least 1 evaluable postbaseline efficacy assessment, and receive $\geq 75\%$ of planned cumulative doses. This is the primary population for efficacy analyses.
PK	Includes All Treated Population with at least 1 available concentration result post-treatment (whichever the cycle and even if dosing is incomplete) with adequate documentation of date and time of dosing and date and time of sampling.
ADA	Includes All Treated Population with at least 1 available ADA result (negative, positive, or inconclusive) post-treatment (whichever the cycle and even if dosing is incomplete).

Abbreviations: ADA = anti-drug antibody, ICF = informed consent form, IMP = investigational medicinal product, PK = pharmacokinetic.

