2 SAMPLE SIZE DETERMINATION

Statistical hypotheses and sample size determination:

Phase 1: There is no formal statistical hypothesis. Approximately 6 to 12 safety evaluable participants are expected to be enrolled.

Phase 2:

- Null hypothesis: True RR [REDACTED]
- Alternative hypothesis: True RR [REDACTED]

With a minimum sample size of 12 participants per cohort and 1-sided alpha of 0.025, the analysis will have at least 80% power to demonstrate that RR is significantly better than [REDACTED] assuming the true RR is [REDACTED], based on exact test. A null hypothesis of [REDACTED] is selected representing placebo control as there is currently no approved or standard therapy for desensitization, and there is no expected decrease in anti-HLA antibody levels or cPRA in patients who do not undergo desensitization therapy.

A maximum of 6 replacements per cohort is allowed for participants who:

- enroll in Phase 1 and receive <90% of the planned cumulative doses within the first cycle (unless they discontinue IMP due to pre-defined unacceptable toxicity), or
- receive <75% of planned cumulative doses within 3 cycles, or
- have consecutive dose interruption of >28 days, or
- do not complete site visit FUP, after agreement with Medical Monitor.

Participants treated at the Phase 2 dose during Phase 1 will be included in the analysis together with the participants in Phase 2.

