3 ANALYSIS POPULATIONS

The following populations for analyses are defined:

Table 3 - Populations for analyses

Population	Description
Screened	All participants who sign the informed consent form (ICF).
Enrolled	Includes all participants from screened population who plan to continue in the treatment phase upon completion of screening, regardless of whether the study intervention (isatuximab) was received or not.
All treated	Includes all participants who receive at least 1 dose of isatuximab-. This population is the primary population for the analyses of safety parameters, unless otherwise noted. All analyses using this population will be based on the dose level actually received.
Safety-evaluable (Phase 1)	Includes all participants enrolled in Phase 1 who receive $\geq 90\%$ planned cumulative doses of isatuximab within Cycle 1 (unless IMP is discontinued due to pre-defined unacceptable toxicity).
Efficacy-evaluable	Includes All Treated population who fulfill the study eligibility criteria, with an evaluable baseline and at least 1 evaluable postbaseline efficacy assessment and receive $\geq 75\%$ of planned cumulative doses. This is the primary population for efficacy analyses.
PK	Includes All Treated population with at least 1 available concentration result post-treatment (whichever the cycle and even if dosing is incomplete) with adequate documentation of date and time of dosing and date and time of sampling.
ADA	Includes All Treated population with at least 1 available ADA result (negative, positive, or inconclusive) post-treatment (whichever the cycle and even if dosing is incomplete).

Participants exposed to isatuximab before or without being enrolled will not be considered enrolled and will not be included in any analysis population. The safety experience of these participants will be reported separately.

Enrolled participants for whom it is unclear whether they took isatuximab will be considered as treated and will be included in the safety population.

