4.2 PARTICIPANT DISPOSITIONS

The number (%) of participants included in each of the analysis populations listed in [Table 3](#) will be summarized.

Screen failures are defined as participants who consent to participate in the study but are not subsequently enrolled. If applicable, the number (%) of screen failures will be provided in the screened population.

Enrolled participants will include screened participants who plan to continue in the treatment phase, ie, those for whom the investigator ticked “Yes” to the question “Will the subject continue in the Treatment phase?” in the Completion of Screening eCRF page.

The number (%) of participants in the following categories will be provided:

- Screened participants, and screen failures (if applicable)
- Enrolled participants

- Enrolled but not treated participants
- Enrolled and treated participants
- Participants who completed the study treatment period as per protocol
- Participants who did not complete the study treatment period as per protocol and main reason for definitive treatment discontinuation
- Participants who completed the site visit follow-up period.
- Participants who did not complete the site visit follow-up period and main reason for site visit follow-up discontinuation
- Participants who completed the study/extended follow-up period.
- Participants who did not complete the study/extended follow-up period and main reason for study/extended follow-up discontinuation
- Participant status at last study contact

If applicable, the number (%) of treated but not enrolled participants will also be presented.

Protocol deviations

Critical and major protocol deviations (automatic or manual) will be summarized in the enrolled and/or treated population.

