4.3.2 Main analytical approach

The primary efficacy analysis is based on a treatment policy estimand introduced in [Section 1.2.1](#).

This primary estimand is defined according to the following attributes:

- The endpoint is RR, as defined in [Section 4.3.1](#).
- The treatment condition of interest is isatuximab
- The analysis population is the efficacy-evaluable population (defined in [Section 3](#))
- The study intervention interruption/discontinuation intercurrent event will be handled with the treatment policy strategy. RR will be assessed based on the 3 criteria irrespective of study intervention interruption/discontinuation.
- Population-level summary will be RR, defined as the proportion of participants meeting at least one of the predefined desensitization efficacy criteria (refer to [Section 4.3.1](#)), along with and two-sided 95% confidence intervals using the Clopper-Pearson method.

Proportion of participants meeting each criterion will also be tabulated.

Calculation details and examples on RR criteria 1 and 2 are provided in Appendix 4, [Section 5.4.2](#) (DESENSITIZATION response criteria).

For RR criterion 3, elimination of anti-HLA-antibody will be determined for each applicable molecular specificity.

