4.7.1.2 IMP exposure

The dose information will be assessed by the following:

- Total number of cycles started
- Number of cycles started per participant

- Duration of IMP exposure (in weeks) is defined as [(last date of IMP administration) – (first date of IMP administration)] / 7.
- The first day of IMP administration is defined as the first administration date with non-zero dose for the IMP. The last date of IMP administration is defined as follows:
 - date of the last IMP dose + 7 if the last cycle is a QW cycle or date of death + 1, whichever is earlier
 - date of the last IMP dose + 14 if the last cycle is a Q2W cycle or date of death + 1, whichever is earlier
- Actual dose (mg/kg): is defined as the actual dose (mg) administered divided by the body weight at the time
- Cumulative dose (mg/kg): the cumulative dose is the sum of all actual doses (mg/kg) of IMP, given from first to last administration
- Actual dose intensity (ADI [mg/kg/week]): defined as the cumulative dose (mg/kg) divided by the duration of IMP exposure (weeks)
- Planned dose intensity (PDI [mg/kg/week]): corresponds to the planned dose (mg/kg) multiplied by the theoretical total number of doses started and divided by the theoretical cycle duration expressed in weeks (ie, 4 weeks per cycle started)
- Relative dose intensity (RDI, in %): $100 \times \frac{\text{ADI (mg/kg/week)}}{\text{PDI (mg/kg/week)}}$

The total number of doses, total number of cycles started, number of cycles started by participant will be summarized as a quantitative variable and by category (number [%] of participants receiving 1 cycle, 2 cycles, 3 cycles). Duration of IMP exposure, cumulative dose, ADI and RDI will be summarized quantitatively.

The following variables will be derived to describe dose modifications:

- Dose reduction: The first IMP administration will not be counted as a dose reduction. For the second and subsequent IMP administrations, dose reduction will be determined using the dose level intervals provided in [Table 4](#), by comparing the current dose level to the previous dose level. If the current dose level is below the dose level interval of the previous dose administration, then the current dose level is considered reduced.

Table 4 - IMP dose reduction criteria

Actual dose level	Dose level interval
Starting dose (10 mg/kg)	>7.5 mg/kg
Dose level -1 (5 mg/kg)	>0 mg/kg and \leq 7.5 mg/kg

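### The primary estimand is labelled treatment policy for discontinuation, but its population requires at least 75% of planned doses, so most early stoppers drop out and no readable analysis shows their responses

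*SAP*

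**What the plan says.** SAP 1.2.1, Table 2, names one intercurrent event for the primary endpoint, interruption or discontinuation of isatuximab, and handles it thus: "Response rate will be analyzed regardless of intervention discontinuation (treatment policy". SAP 4.3.2 repeats the rule: "RR will be assessed based on the 3 criteria irrespective of study intervention interruption/discontinuation".

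Both places name the Efficacy-evaluable population as the estimand's population. Protocol 9.3 (Table 8) admits treated participants who meet eligibility, "with an evaluable baseline and at least 1 evaluable postbaseline efficacy assessment, and receive" at least 75% of planned cumulative doses. SAP 3 (Table 3) has the same threshold, 75% "of planned cumulative doses. This is the primary population for efficacy analyses". Neither row states a period or a unit. The replacement rule in SAP 2 and protocol 9.2 uses the complementary threshold and does give a period: "receive <75% of planned cumulative doses within 3 cycles, or".

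For the primary endpoint, the only sensitivity analysis (SAP 4.3.3) reassigns cohorts by central-laboratory cPRA within the same population. Supplementary analyses (SAP 4.3.4) are marked as not applicable. SAP 4.2 will report the number in each analysis population and "Participants who did not complete the study treatment period as per protocol and main reason for definitive treatment discontinuation".

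**The concern.** A treatment-policy strategy counts a participant's outcome whether or not treatment was stopped. A population defined by how much treatment was received removes people because they stopped. When both sit in one estimand, the population rule acts first, and the strategy has little left to act on.

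The exclusion need not be neutral. The Phase 1 Safety-evaluable definition keeps participants who stop for pre-defined unacceptable toxicity; the Efficacy-evaluable definition has no such exception. Participants who go to transplant during treatment must stop isatuximab, so an early transplant can also lead to exclusion. An under-dosed participant can still be a responder, since eliminating one anti-HLA antibody is enough. The direction of any effect therefore cannot be predicted, and the responses of those excluded need to be seen.

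At stake is what the reported rate describes: participants who were dosed nearly as planned, under a label that a reader will take to include those who were not.

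**Working it through.** **Plan's own figure.** The stated power (at least 80%, 12 per cohort, one-sided 0.025, exact test) cannot be reproduced because the null and alternative rates are blacked out. That is not a fault of the plan, and this point does not depend on it.

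**Step 1: who the threshold removes.** Protocol Table 4 plans 4 + 2 + 2 = 8 infusions over three cycles, and 75% of 8 is 6.

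| Stops after infusion | Share of 8 | In population |
|---|---|---|
| 1 | 12.5% | no |
| 2 | 25.0% | no |
| 3 | 37.5% | no |
| 4 | 50.0% | no |
| 5 | 62.5% | no |
| 6 | 75.0% | yes |
| 7 | 87.5% | yes |
| 8 (complete) | 100% | yes |

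Treatment policy can therefore act only on stops after infusion 6 or 7, and on delays or interruptions among those who still reach 75%.

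**Step 2: period and unit (minor).** The three-cycle reading comes from the replacement rule. SAP 4.7.1.2 computes planned dose intensity differently, "divided by the theoretical cycle duration expressed in weeks (ie, 4 weeks per cycle started". Applied to the threshold, that basis would keep someone who stops after infusion 4 (4/4 = 100%) or infusion 5 (5/6 = 83.3%). On the unit, SAP 4.7.1.2 says "the cumulative dose is the sum of all actual doses (mg/kg) of IMP, given from first to last administration". In mg/kg, five full infusions and one half infusion give 5.5/8 = 68.75% and fail; counted as six infusions they give 75% and pass.

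**Step 3: whether the data would exist.** Protocol 7.1.1 keeps participants who stop for reasons other than transplantation in site visit follow-up. The Schedule of Activities starts that follow-up about 15 days after the last dose, with central cPRA and SAB draws every 4 weeks, and has an early discontinuation draw for those who leave the study. Most early stoppers should have at least one post-baseline central sample.

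**Step 4: possible size.** Let x of 12 evaluable participants respond and let k treated participants be excluded. Restoring them gives a rate between x/(12+k), if none responded, and (x+k)/(12+k), if all did. The width is k/(12+k), whatever x is. Illustration with x = 6, where 6/12 = 50.0% (Clopper-Pearson 95% CI 21.1% to 78.9%):

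| k | Lowest | Highest | Width (points) |
|---|---|---|---|
| 1 | 6/13 = 46.2% | 7/13 = 53.8% | 7.7 |
| 2 | 6/14 = 42.9% | 8/14 = 57.1% | 14.3 |
| 3 | 6/15 = 40.0% | 9/15 = 60.0% | 20.0 |

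The interval for 6/12 is 78.9 − 21.1 = 57.8 points wide, so each of these spans is well inside the sampling uncertainty.

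**The case against.** The strongest defence is disclosure. Table 2 names the Efficacy-evaluable population in the same row as the treatment-policy rule, and SAP 4.3.2 lists both as attributes of one estimand. The SAP nowhere claims an all-treated rate. The population is set by the protocol, matches the replacement rule, and suits a single-arm study of preliminary efficacy reported descriptively. Protocol 7.1.1 expects permanent discontinuation to be rare. Disposition tables will give counts and reasons, so a reader can work out bounds like those above.

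Most of this stands and limits the point. It does not reconcile the label with the population, and bounds do not replace observed responses.

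A reader might infer four stronger things that the documents do not support:

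- *That the threshold has no usable definition.* The replacement rule uses the same phrase over three cycles. The rival basis of cycles started comes only from a dose-intensity formula for exposure summaries. The unit question needs a partly given infusion at exactly the threshold, and protocol 6.6.1 allows no dose reduction.
- *That the SAP hides the restriction.* It names the population and will report its size.
- *That the response rate is inflated.* The direction is unknown.
- *That no analysis of those excluded exists anywhere.* The exploratory efficacy section (SAP 4.5) is redacted, so only the readable text can be judged.

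**Conclusion.** The estimand label is wrong as written, and a cheap improvement is available. As planned, the primary response rate and its exact interval are conditional on the Efficacy-evaluable criteria, including at least 75% dosing. Discontinuation is disregarded only within that group, and most early discontinuation falls outside it. No readable primary-endpoint analysis shows how those excluded responded.

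The conclusion about who is removed assumes the three-cycle reading and counting by infusions. The sizes assume 12 evaluable participants and an arbitrary k; they are bounds, not forecasts. If discontinuation is as rare as the protocol expects, the effect may be small. The effect on the exact test cannot be assessed while the null rate is redacted. Confidence is high in the mismatch and low in its numerical consequence.

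**What to change.** 1. In SAP 1.2.1 and 4.3.2, state that the primary response rate is conditional on the Efficacy-evaluable criteria, including at least 75% dosing, and that treatment policy applies only within that population. As a minor clarification, carry the three-cycle period into the definition in SAP 3 and name the unit (infusions or mg/kg).
2. In SAP 4.3.4, add a supplementary response rate by cohort with Clopper-Pearson intervals. Base it on All Treated participants at the Phase 2 dose with an evaluable baseline, including those who were replaced, using all observed central samples. Show it two ways: among those with at least one evaluable post-baseline sample, and with those lacking one counted as non-responders. The second is an imputation convention that departs from the non-missing denominator in SAP 5.4.1, and should be described as such. List separately anyone transplanted before a post-baseline sample, so that they are not read simply as treatment failures.
3. Keep the Efficacy-evaluable analysis as primary. Record the change in SAP 5.2 and state that it was specified after the interim analysis of 26-Aug-2021 given in the SAP version history.

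The cost is a few sentences and one table from samples already scheduled; the sample size and power statement are untouched. The downside is that the added rate may be less favourable, and that it would be specified after some open-label data had been seen.
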